10.3. Serious adverse event and new information notification (responsibility of the investigator)

Serious adverse events, regardless of relationship to the study drugs, will be reported by the investigator in the patient's CRF.

The investigator will notify to the Vigilance Unit without delay about any serious adverse events or new events occurring:

- From the date of the informed consent is signed,
- During the whole patient treatment period as defined by the research,
- Until 90 days after the last dose of the IMP/studied treatments or until the start of a new antitumor therapy, whichever occurs first,
- Beyond this period of time, only those SAEs suspected to be related to the IMP or the research (other treatments used, diagnostic procedures, examinations carried out during the research) will be collected without any limitation in terms of deadline. Nonetheless, the Sponsor will evaluate any safety information related to the clinical trial that is spontaneously reported by an Investigator beyond the time frame specified in the protocol.
- Whenever possible the investigator will record the main diagnosis instead of the signs and symptoms.

Type of Event	Reporting procedure	Deadline for reporting to the sponsor
SAE	SAE Notification form + written report form if necessary	To be reported immediately to the sponsor
New information	Written report form	To be reported immediately to the sponsor
Pregnancy	Pregnancy Notification form + Written report form if necessary	As soon as pregnancy is confirmed

The investigator must complete the "Serious Adverse Event Notification Form" (Appendix 5) immediately, in English, and assess the relationship with the study treatment. The form must then be dated, signed and sent by fax to the following address without delay to:

CELLULE DE VIGILANCE (VIGILANCE UNIT) – R&D UNICANCER

[contact]

Or contact : R&D Unicancer – Mail : [name]

For each event, the investigator will record:

- A description of the event that is as clearly as possible, using medical terminology,
- Date AE met criteria for serious AE, the date the event ended
- Date of the serious adverse event notification form report - The steps taken and whether or not corrective treatment was required, whether or not the investigational treatment was discontinued, etc.
- Date of hospitalization
- Date of discharge
- Probable cause of death
- Date of death
- Autopsy performed
- The patient's relevant medical history
- Concomitant medications / therapies
- The causal link between this event and the trial treatment, disease treated or an intercurrent disease or treatment, or any obligation imposed by the research (a treatment-free period, additional examinations requested as part of the research etc.) :
 - ✓ Causality assessment in relation to all study medications
 - ✓ Causality assessment in relation to Study procedure(s)
 - ✓ Causality assessment in relation to Additional Study Drug

- ✓ In addition, when applicable, the investigator must also indicate if this event is related to disease progression.
- Clinical course. If the event was not fatal, it should be monitored until recovery, until the patient has returned to his/her previous condition, or until any sequelae have stabilized,
- Whenever possible, the investigator must also attach the following with the serious adverse event report:
 - A copy of the hospitalization or extended hospitalization report,
 - A copy of the autopsy report, if required,
 - A copy of all the results of any additional tests performed, including relevant negative results, along with the normal laboratory values,
 - Any other document he or she considers useful and relevant.

All these documents must be anonymized. Additional information may be requested (by fax, by telephone or during a visit) by the CRA and/or by the Vigilance Unit using a follow-up request form.

The investigator is responsible for providing appropriate medical follow-up for patients until resolution or stabilization of the adverse event or until the patient's death. Sometimes this may mean that follow-up will extend beyond the patient's withdrawal from the trial.

The investigator keeps the documents about the presumed adverse effect so that the information previously sent can be added to if necessary.

The investigator responds to requests for additional information from the Vigilance Unit in order to document the original observation.

New cancers : the development of a new cancer should be regarded as an SAE. New primary cancers are those that are not the primary reason for the administration of the IP and have been identified after the patient's inclusion in this study.

10.4. Reporting pregnancy cases occurred within the clinical trial

Pregnancy and suspected pregnancy (including a positive pregnancy test regardless of age or disease state) of a female patient or the female partner of a male patient occurring while the patient is on study drug, or within 90 days from the patient's discontinuation visit, are considered immediately reportable events.

The Investigator will report the following events immediately and always within 24 hours from first knowledge:

- Any occurrence of a pregnancy where any kind of exposure to the IMP is suspected,
- Possible exposure of a pregnant woman (this could involve a partner of a male patient or a pregnant female who came in contact with the clinical trial IMP),
- All reports of elevated/questionable or indeterminate beta human chorionic gonadotropins (β -hCGs).

Immediately after detecting a case of suspected pregnancy in a female clinical trial patient, the decision on her continued participation in the clinical trial will be jointly taken by the trial patient, the Investigator and the Sponsor, with the patient's best interest in mind. A decision to continue the pregnancy will require immediate withdrawal from the trial.

Any pregnancy, suspected pregnancy, or positive pregnancy test must be reported to the Vigilance Unit immediately by facsimile using the Pregnancy Report form (appendix 7). In the case of pregnancy of the female partner of a trial patient, the Investigator will obtain her consent to provide the information in these situations.

The Investigator will follow the pregnancy until its outcome, and must notify the Vigilance Unit the outcome of the pregnancy within 24 hours of first knowledge as a follow-up to the initial report.

For any event during the pregnancy which meets a seriousness criterion (including fetal or neonatal death or congenital anomaly) the Investigator will also follow the procedures for reporting SAEs (complete and send the SAE form to the Vigilance Unit by facsimile within 24 hours of the Investigator's knowledge of the event).

All neonatal deaths that occur within 90 days of birth should be reported, without regard to causality, as SAEs. In addition, any infant death at any time thereafter that the Investigator suspects is related to the exposure to the study drug/IMP should also be reported to the Vigilance Unit by facsimile within 24 hours of the Investigators' knowledge of the event.

Whenever possible, the investigator must also attach the following with the serious adverse event report:

- A copy of the hospitalization or extended hospitalization report,
- A copy of the autopsy report, if required,
- A copy of all the results of any additional tests performed, including relevant negative results, along with the normal laboratory values,
- Any other document he or she considers useful and relevant.

All these documents must be anonymized.

Additional information may be requested (by fax, by telephone or during a visit) by the Vigilance Unit.

10.5. Report of Overdose

An overdose is defined as a subject receiving a dose of durvalumab in excess of that specified in the Investigator's Brochure, unless otherwise specified in this protocol.

Any overdose of a study subject with durvalumab and/or trabectedin, with or without associated AEs/SAEs, is required to be reported within 24 hours of knowledge of the event to the sponsor. If the overdose results in an AE, the AE must also be recorded as an AE. Overdose does not automatically make an AE serious, but if the consequences of the overdose are serious, for example death or hospitalization, the event is serious and must be recorded and reported as an SAE. There is currently no specific treatment in the event of an overdose of durvalumab.

The investigator will use clinical judgment to treat any overdose.

10.6. Report of Hepatic function abnormality

Hepatic function abnormality (as defined by cases where a subject shows an AST or ALT $\geq 3 \times \text{ULN}$ and total bilirubin $\geq 2 \times \text{ULN}$ in a study subject, with or without associated clinical manifestations, is required to be reported as "hepatic function abnormal" within 24 hours of knowledge of the event to the sponsor using the SAE form unless a definitive underlying diagnosis for the abnormality (e.g., cholelithiasis or bile duct obstruction) that is unrelated to investigational product has been confirmed.

Hy's Law: Cases where a patient shows elevations in liver biochemistry may require further evaluation and occurrences of AST or ALT $\geq 3 \times \text{ULN}$ together with total bilirubin $\geq 2 \times \text{ULN}$ may need to be reported as SAEs. Please refer to Appendix 4, the Toxicity Management Guidelines, for further instruction on cases of increases in liver biochemistry and evaluation of Hy's law.

- If the definitive underlying diagnosis for the abnormality has been established and is unrelated to investigational product, the decision to continue dosing of the study subject will be based on the clinical judgment of the investigator.
- If no definitive underlying diagnosis for the abnormality is established, dosing of the study subject must be interrupted immediately. Follow-up investigations and inquiries must be initiated by the investigational site without delay.

10.7. Reporting events of clinical interest and immune-mediated adverse events

Information on how to identify and evaluate imAE/imAEs has been developed and is included in appendix 4. All imAE imAEs should be reported to sponsor.

ImAE observed with durvalumab include:

- Colitis, Intestinal perforation
- Pneumonitis
- ALT/AST increases / hepatitis / hepatotoxicity

Increase of AST and ALT should be reported as event of clinical interest if it meets the criteria of seriousness such as hospitalization and especially if treatment was given because of the event.

- Neuropathy / neuromuscular toxicity (i.e. events of encephalitis, peripheral motor and sensory neuropathies, Guillain-Barré, and myasthenia gravis)

- Endocrinopathy (i.e. events of hypophysitis, adrenal insufficiency, and hyper- and hypothyroidism, type I diabetes mellitus)
- Dermatitis
- Nephritis
- Pancreatitis (or labs suggestive of pancreatitis - increased serum lipase , increased serum amylase)
- Rash / dermatitis (including Stevens-Johnson syndrome, toxic epidermal necrolysis, rashes complicated by dermal ulceration or necrotic, bullous or haemorrhagic manifestations)
- Myositis/Polymyositis
- Vasculitis
- Non-infectious meningitis
- Non-infectious encephalitis
- Other inflammatory responses that are rare with a potential immune-mediated aetiology include, but are not limited to, myocarditis, pericarditis, uveitis, haematological events, sarcoidosis and rheumatological events.

In addition, infusion-related reactions and hypersensitivity/anaphylactic reactions with a different underlying pharmacological etiology are also considered AESIs.

The investigator will notify the Vigilance Unit without delay about any events of clinical interest.

The investigator must complete the specific form (Appendix 6) immediately, in English. The form must then be dated, signed and sent by fax to the following address without delay to:

CELLULE DE VIGILANCE (VIGILANCE UNIT) – R&D UNICANCER

[contact]

Or contact : R&D Unicancer – Mail : [name]

Adverse events that are both an SAE and an imAEimAEs should be reported one time as an SAE only, however the event should be appropriately identified as an imAEimAEs too in the database.

10.8. report of Non serious adverse event

TYPE OF EVENT	REPORTING PROCEDURES	DEADLINE FOR REPORTING TO THE SPONSOR
Non-serious AE	Case report/record form	Does not need to be reported immediately

Non-serious adverse events will be reported by the investigator in the patient's CRF and will be followed up until complete resolution.

If an adverse event becomes serious, it should be reported and followed-up as mentioned in the previous reporting procedures.

If the investigator wishes to decrease the trial treatment dose or temporarily stop the study management without respecting protocol procedures, he/she should previously discuss it with the coordinator.

However, symptomatic treatment can be prescribed to manage the adverse event.

Any definitive interruption of the procedure has to be immediately notified to the sponsor. The patient remains in the study and is followed-up according to the procedures described in the protocol.

10.9. Responsibility of Vigilance Unit

The Vigilance Unit will analyze each SAE to define:

- The relationship with the study treatment,
- The listedness/expectedness according to the most updated reference safety information of the studied IMP:
 - Investigator's Brochure (IB) for the Durvalumab (MEDI4736)
 - and Summary Product Characteristic (SmPC) for the Trabectedine (Yondelis®).

10.10. Notification and registration of unexpected serious adverse events and new information (responsibility of the sponsor)

The sponsor notifies unexpected serious adverse events and new information to the Regulatory Authorities (in person, or through an organization which has received allowances for this task) according to the usual notification procedures.

CONFIDENTIAL

11. QUALITY ASSURANCE AND TRIAL MONITORING

11.1. Monitoring of the trial

11.1.1. *Steering Committee*

The study will be supervised and monitored by a steering committee comprising members participating in the study:

- Dr. [name], Coordinating Investigator and Chairman of the committee.
- Dr. [name], Scientific responsive, medical oncologist.
- A representative of the sponsor (Pr [name] or a substitute).
- The biostatistician of the trial (Ms. [name], or a substitute).
- The pharmacist of the trial (Ms. [name], or a substitute).

This committee must ensure the following:

- Implementation and regular follow-up of the study
- Patient protection,
- That the trial is conducted ethically, in accordance with the protocol,
- That the trial benefit/risk ratio is evaluated and the scientific results are checked during or at the end of the trial.

For the dose escalation part, the steering committee will be consulted before proceeding or not to the next dose level.

In addition, the steering committee will resolve any specific issue regarding the DLT status. Note however, that medical oncologists of the steering committee cannot comment on the DLT status of patients they have been in charge of. In such case, the opinion of another medical oncologist who has not treated the patient will be sought.

The steering committee decides on any relevant amendment to the protocol that is required in order to continue the trial (protocol amendments prior to submission to the EC and the relevant Health Authorities, decisions on whether to open or close research sites, discussion of results and the strategy for the publication of these results). It must inform the sponsor of any decisions taken. Decisions concerning a major amendment or a change to the budget must be approved by the sponsor.

11.1.2. *Independent Data Monitoring Committee*

- An independent data monitoring committee (IDMC) will be created at the request of the relevant Authority, the sponsor or the steering committee. The IDMC plays an advisory role for the Sponsor, who has the final decision regarding the implementation of recommendations put forward by the IDMC.
- Conclusions of the steering committee for the MTD definition based on the dose escalation trial will be submitted for approval to the IDMC before opening the expansion cohorts. If necessary, a second IDMC may be set up at the end of the expansion cohorts.
- Implementation of the IDMC committee will be performed according to the internal procedures at Institut bergonié.

Composition of the IDMC

- This Committee must comprise at least one qualified oncologist, one pharmacologist and one statistician:
 - Qualified oncologist (Pr [name])
 - Pharmacologist ([name])
 - Statistician ([name])
- All of whom will have experience in the monitoring and analysis of clinical trials. One of these members will be appointed as the Trial Rapporteur.
- Each of these members must be unconnected with the trial and cannot, therefore, be one of the trial investigators.
- These members are appointed by the Sponsor in consultation with the trial co-ordinator and the steering committee.

Responsibilities of the IDMC

The IDMC is responsible for the following:

- Analyzing preliminary efficacy and safety data;
- Making recommendations on the continuation, early discontinuation (in the case of toxicity) or publication of the trial results;
- Drafting the minutes after each meeting and monitoring their confidentiality.

Any recommendation from the IDMC that can be made public will be announced by the Sponsor and not by the steering committee. The Sponsor is responsible for sending IDMC recommendations to the regulatory authorities [ANSM (French Agency for the Safety of Health Care Products) and EMEA (European Medicines Evaluation Agency)].

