3.4. EXPANSION cohorts

- Once the MTD has been defined based on the dose escalation study, the expansion cohorts will be opened. All patients will be treated at the MTD of Trabectedin (as defined in the escalation trial) given in association with durvalumab with the same schedule as in the phase I trial.
- Following the expansion cohorts, the RP2D for Trabectedin will be identified by the steering committee based on safety data from patients included in the dose escalation part and the expansion cohorts, as well as PD data. Data from all patients (escalation + expansion cohorts) will be used to define the RP2D.

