6.7. Dosing delays/dose modifications and adverse event management

No changes in durvalumab dose are allowed. If immune related adverse events occur, the durvalumab administration will be adjusted (delayed doses) as per the toxicity management guidelines (Appendix 4).

Dose escalation: Toxicities that would lead to dose modification should be discussed with the sponsor.

Expansion cohorts: Doses will be reduced for haematological and other adverse events. Dose adjustments are to be made according to the greatest degree of toxicity. Adverse events will be graded using the NCI Common Terminology Criteria for Adverse Events Version 4.03 (NI-CTCAE).

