9.1.1. Phase I (Expansion cohorts)

- The primary objective is to determine preliminary signs of anti-tumor activity of trabectedin given in combination with DURVALUMAB among two selected cohorts of patients (STS and ovarian carcinomas) in terms of objective response under treatment as per RECIST v1.1 criteria.
- Once the Maximum Tolerated Dose (MTD) is established for trabectedin, 2 distinct cohorts will be treated at the MTD:
 - Cohort A: patients with advanced STS.
 - Cohort B: patients with advanced ovarian carcinomas
- For each cohort:
 - Sample size is calculated based on the first stage of a 2-stage Gehan design assuming a 20% efficacy rate, 5% false positive rate and 10% precision (Gehan 1961).
 - 14 eligible and assessable subjects are required.
 - If at least one objective response (CR or PR as per RECIST v1.1) is observed under treatment, the study drug association will be considered worthy of further testing in this indication.

Assuming 10% patients not eligible or that cannot be assessed for the primary endpoint, **15 patients will be recruited for each of the 2 cohorts**, i.e. a total of **30 patients will be included in the expansion cohorts**.

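### Thirty expansion patients are treated at a dose cleared on at most six, with no scheduled safety review and no pre-specified toxicity threshold

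*Protocol*

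**What the plan says.** **Escalation.** Protocol 3.3.2 enters 3 to 6 patients per level. Escalation stops at 2 or more DLTs, and a level with at least 2/3 or 2/6 is the maximum administered dose (MAD). The MTD is the highest dose with no more than 1 DLT in 6 over 21 days. Protocol 11.1.1 adds a timed check: "For the dose escalation part, the steering committee will be consulted before proceeding or not to the next dose level". The independent data monitoring committee (IDMC) approves the MTD before expansion opens (Protocol 9.3 and 11.1.2).

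**Expansion.** Protocol 9.1.1 states that "30 patients will be included in the expansion cohorts", and Protocol 3.4 that "All patients will be treated at the MTD of Trabectedin (as defined in the escalation trial"). For toxicity in this part, Protocol 6.7 states: "Doses will be reduced for haematological and other adverse events". The recommended phase II dose is chosen only after the expansion cohorts (Protocol 3.4).

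**Oversight during expansion.** The one further IDMC named in Protocol 11.1.2 is conditional and late: "If necessary, a second IDMC may be set up at the end of the expansion cohorts". The IDMC's listed responsibilities include "Making recommendations on the continuation, early discontinuation (in the case of toxicity) or publication of the trial results". The steering committee's benefit/risk evaluation may take place during the trial or at its end (Protocol 11.1.1). SAP 4.1 lists outputs for each allocated dose, and SAP 4.2 lists outputs at the end of escalation and at the end of expansion. None is listed for a point within expansion.

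**The concern.** The timed controls stop where the larger exposure begins. Six patients say little about a DLT rate, so expansion is the main test of whether the MTD is tolerable. Two features of the plan add weight. Protocol 1.5 anticipates overlapping transaminitis, and the Synopsis adds a third centre that treated no escalation patients.

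Dose reductions under Protocol 6.7 and 6.7.1.2 act on one patient's later cycles. They do not change the dose at which the next patient starts, and they add nothing up across patients. Without a dated cumulative review, an excess of DLT-type events could build up over the whole of expansion before anyone is required to look at it as a rate. At stake are the safety of 30 patients and the basis for the recommended phase II dose, which is part of the primary objective.

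**Working it through.** **1. The plan's own sample size.** Protocol 9.1.1 uses the first stage of a Gehan design, "assuming a 20% efficacy rate, 5% false positive rate and 10% precision", and concludes that "14 eligible and assessable subjects are required" per cohort. The smallest n with 0.8^n ≤ 0.05 is 14 (0.8^13 = 0.055, 0.8^14 = 0.044), so 14 reproduces. Allowing 10% loss gives 14/0.9 = 15.6, against 15 recruited per cohort and 30 in total. This calculation concerns response only. No toxicity criterion enters it.

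**2. How well 6 patients screen a dose.** The true rates below are assumptions, because the documents give none. For a level already reached with 6 assessable patients, P(at most 1 DLT) = (1−p)^6 + 6p(1−p)^5:

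- p = 1/3: 0.088 + 0.263 = 0.351
- p = 0.40: 0.047 + 0.187 = 0.233
- p = 0.50: 0.016 + 0.094 = 0.109

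The exact (Clopper-Pearson) 95% interval for 1/6 is 0.4% to 64%. The upper limit after 0/6 is 46%. With 30 patients starting at such a dose, the expected number with a cycle 1 DLT is 30p = 10, 12 or 15.

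**3. What a scheduled review could do.** Three illustrative rules are shown, with both cohorts pooled. The probabilities are exact: the cumulative DLT count is carried from look to look with binomial increments, and every path that reaches the limit is removed. The limits are cumulative DLT counts at each look.

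| Rule | Pause at 1/3 | at 0.40 | at 0.50 | False pause at 1/6 |
|---|---|---|---|---|
| Above 1/3: 3/6, 5/12, 7/18, 9/24 | 58% | 79% | 96% | 9% |
| Plan's MAD proportion, 2/6 or more: 2/6, 4/12, 6/18, 8/24 | 81% | 93% | 99% | 30% |
| Two looks: 4/10, 6/20 | 73% | 89% | 98% | 13% |

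False pauses at a true rate of 1/6, summed over the four looks:

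- First rule: 0.062 + 0.016 + 0.006 + 0.002 ≈ 0.087 (before rounding of the terms).
- Second rule: 0.263 + 0.028 + 0.008 + 0.003 ≈ 0.303.

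At a true rate of 0.40, the mean number treated before a pause, or 30 if there is none, is 14.4 under the first rule and 15.0 under the third. These means ignore patients entered while the last patient of a block completes cycle 1.

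**4. Feasibility.** Enrolment is about 18 months in Protocol 4.3 and 30 months in the Synopsis. Assume that all 50 patients accrue evenly. The rate is then 50/18 = 2.8 or 50/30 = 1.7 per month, so 30 expansion patients take 10.8 to 18 months. About 1.1 to 1.9 patients enter per 21 days. A review after each block of 6 would not be overtaken by accrual.

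**The case against.** A reader might infer that no committee can act during expansion, or that a too-toxic dose would certainly reach all 30 patients. The documents do not support either reading.

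- Protocol 11.1.2 lets the authority, the sponsor or the steering committee request an IDMC, with no time limit. Naming an optional one at the end does not exclude an earlier one.
- The steering committee is charged with regular follow-up and patient protection (Protocol 11.1.1).
- Serious adverse events and new safety information are reported at once (Protocol 10.3). Any grade 4 laboratory result counts as serious (Protocol 10.2.2). New information includes data that could lead to suspension of the research (Protocol 10.2.7).
- Data are monitored remotely in real time (Protocol 11.2.1).

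All of this stands, and an ad hoc stop is possible. But none of it carries a date or a cumulative limit. The Vigilance Unit analyses each serious event for relationship and expectedness (Protocol 10.9), not as a running rate.

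A second tempting reading is that a pause above 1/3 applies the plan's own limit, so that its 9% false-pause risk is the cost of using that limit. It does not. The plan already classes 2/6 as MAD, and a rule at that proportion pauses falsely 30% of the time at 1/6.

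Two practical objections also have force. DLT incidence is an endpoint of the escalation part only (Protocol 8.1, SAP 3.2.3), so expansion events would need adjudication for relatedness, duration and transaminitis. Efficacy is analysed by cohort (Protocol 9.3.2.2), so pooling for safety needs a reason. The reason is that both cohorts receive the same dose and schedule.

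**Conclusion.** The gap is real: there is no scheduled safety review and no pre-specified toxicity threshold for the 30 expansion patients, and the only further IDMC named comes too late to protect them. The supported conclusion is that an over-toxic MTD could be given to all 30, not that it would be.

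The chance that 6 patients clear such a dose is 35%, 23% or 11% at true DLT rates of 33%, 40% or 50%. These figures rest on assumed rates, on the level having been reached, and on 6 assessable patients. Patients replaced under Protocol 9.2.1 add some exposure that is not counted here.

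The benefit of a scheduled review does not hang on one boundary. At a true rate of 40% the three rules pause accrual with probability 79% to 93%. They differ mainly in false pauses, and that trade-off is for the sponsor and committees. A cycle 1 review would not capture late immune-mediated events, which Protocol 6.7.2 says can arise months after the last dose. This is a low-cost improvement that should be made.

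**What to change.** In Protocol 3.4 and 11.1:

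1. Schedule a cumulative review of cycle 1 DLT-criteria events during expansion, for example each time 6 further patients complete cycle 1. Pool the cohorts for the decision and also show the counts by cohort.
2. Fix a threshold before expansion opens. The sponsor and committees choose it, with its operating characteristics stated. The rules tabulated above are illustrations, not recommendations.
3. Move the second IDMC from the end of expansion to during it, convened when the threshold is crossed. Pause new inclusions until the steering committee, with IDMC advice, decides on accrual.
4. Add the matching review table to the SAP.

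The review governs accrual only. It changes no dose and no individual patient's management.

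**Cost.** A protocol amendment, up to four short tables with looks every 6 patients, using committees already described and adverse event data already collected, and DLT adjudication for expansion patients. At a true DLT rate of 1/6 there is a 9% to 30% chance of an unnecessary temporary pause, depending on the rule.
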